**CRM1 inhibition sensitizes drug resistant human myeloma cells to topoisomerase II inhibitors both in vitro and ex vivo.**

Selective Inhibitors of Nuclear Export / SINE™ compounds (Figure 6) prevent CRM1-mediated export of p53 and topoisomerase II $\alpha$  (topo II $\alpha$ ) (Figure 7). SINE™ compounds CRM1-inhibiting activity was verified by nuclear-cytoplasmic fractionation and immunocytochemical staining of the CRM1 cargoes p53 and topo II $\alpha$  in MM cells (Figure 7). We found that SINE™ molecules reduced cell viability and induced apoptosis when used as both single agents in the sub-micromolar range and when combined with doxorubicin, bortezomib, or carfilzomib but not lenalidomide, melphalan, or dexamethasone (Figure 8 and 9). The anti-cancer effect of SINE™ compounds/doxorubicin was also validated in a drug-resistant stromal cell culture model (Figure 10). Drug resistance induced by co-culture of myeloma cells with bone marrow stroma cells was circumvented by the addition of SINE™ molecules (Figure 10). In addition, CRM1 inhibition sensitized MM cell lines and patient myeloma cells to doxorubicin, bortezomib, and carfilzomib but did not affect peripheral blood mononuclear or non-myeloma bone marrow mononuclear cells as shown by cell viability and apoptosis assay (Figure 11). These preclinical studies showed that SINE™ molecules may be effective against MM in combination with drugs used to treat myeloma such as doxorubicin. Using both human MM cell lines and patient bone marrow samples, we found that SINE™ molecules were effective both as single agents and when combined with the chemotherapeutic drugs doxorubicin, bortezomib, or carfilzomib but not lenalidomide, melphalan, or dexamethasone. These data support the ongoing development of these small-molecule CRM1 antagonists in patients with MM.

[figure not shown]
**Figure 6. CRM1-targeted nuclear export inhibitors.** Similar in mechanism to LMB, the SINE™ CRM1 inhibitors (KPT-127, KPT-185, KPT-249, KPT-276, and KPT-330 (Selinexor)) bind to the active site (CRM1 cysteine residue 528) and prevent transport receptor binding to the cargo protein. KPT-185T is the inactive trans-isomer of KPT-185.

[figure not shown]
**Figure 7. CRM1, p53, and topo II $\alpha$  localization in SINE™ compound-treated cells. A) Immunofluorescence microscopy.** Human H929 MM cells were treated with SINE™ compound or leptomycin B for 20 hours. Samples assayed for p53 and CRM1 were treated with 100 nM SINE™ compound and 10 nM LMB. Samples assayed for topoisomerase (topo) II $\alpha$  were treated with 300 nM SINE™ compound and 100 nM LMB. Intracellular localization and expression of p53, CRM1, and topo II $\alpha$  were examined by immunofluorescence

microscopy. Nuclei were counter-stained using DAPI (blue). **Column 1:** CRM1 (green) nuclear localization in low-density log-phase cells ( $2 \times 10^5$ /ml) was increased in untreated controls, in KPT-185T treated cells, and in LMB-treated cells, but not in KPT-185, KPT-249, or KPT-330 treated cells. **Column 2:** p53 (red) was exported from the nucleus in low-density log-phase ( $2 \times 10^5$ /ml) untreated control, and KPT-185T treated cells; however, cells treated with KPT-185, KPT-249, KPT-330, and LMB had increased nuclear accumulation of p53. **Column 3:** high-density ( $3 \times 10^6$ /ml) untreated control cells exported topo II $\alpha$  (green) to the cytoplasm (as did KPT-185T treated cells) and had low levels of topo II $\alpha$  in the nuclei (blue/DAPI). KPT-185, KPT-249, KPT-330, and LMB prevented nuclear export of topo II $\alpha$ ; therefore, the nuclei were green (topo II $\alpha$ ).

[figure not shown]
**B) CRM1, p53, and topo II $\alpha$  protein expression in SINE™ compound -treated cells.** H929 cells were treated with 100 nM of each CRM1 inhibitor for 20 hours at high-density ( $3 \times 10^6$ /ml) growth conditions. Whole cell lysates assayed for topo II $\alpha$  protein demonstrated minimal change in total amount of topo II $\alpha$ ; however, cytoplasmic fractions showed that the nuclear export of topo II $\alpha$  was inhibited by KPT-185, KPT-249, and LMB. GAPDH protein (loading control) showed that equal amounts of protein were loaded for topo II $\alpha$ . H929 cells were also treated with 100 nM of each CRM1 inhibitor for 20 hours at log-phase growth conditions. Whole cell lysates assayed for p53 showed that total cellular p53 increased in cells treated with CRM1 inhibitors when compared to untreated and KPT-185T treated control samples. Nuclear fractions isolated from treated cells and assayed by Western blot demonstrated that nuclear p53 increased when cells were exposed to the active CRM1 inhibitors KPT-185, KPT-249, and LMB. KPT-185 and KPT-249, but not LMB or KPT-185T, decreased CRM1 protein expression in whole cell lysates. However, when cells were treated with the proteasome inhibitor bortezomib, CRM1 protein levels did not decrease. Treated cells were also assayed for CRM1 mRNA levels. We found that all CRM1 inhibitors had significantly ( $P < 0.05$ ) increased mRNA levels as compared to untreated and KPT-185T treated controls.

**Figure 8. SINE™ compound molecules work synergistically with doxorubicin, bortezomib, and carfilzomib in H929 cells.** SINE™ compound KPT-185 was serially diluted, added to the wells containing H929 MM cells grown at plateau densities ( $2 \times 10^6/\text{ml}$ ), and incubated overnight at  $37^\circ\text{C}$  and  $5\% \text{CO}_2$ . Doxorubicin (A), bortezomib (B), carfilzomib (C), lenalidomide (D), dexamethasone (E), and melphalan (F) were serially diluted and added the following day, and the plates were incubated an additional 24 hours. Samples were assayed for cell viability (CellTiter-Blue reagent) in replicates of 2-4. Percent viability versus drug concentration was plotted. SINE™ compounds were found to be synergistic with doxorubicin ( $\text{CI}=0.377$ ), bortezomib ( $\text{CI}=0.410$ ), and carfilzomib ( $\text{CI}=0.322$ ), additive with melphalan ( $\text{CI}=0.849$ ), and non-synergistic/antagonistic for lenalidomide ( $\text{CI}>2.0$ ) and dexamethasone ( $\text{CI}>2.0$ ) in H929 cells.

[figure not shown]

**Figure 9. Human myeloma cells are sensitized to doxorubicin.** High-density ( $3.0 \times 10^6$  cells/ml) H929 cells were treated concurrently with 300 nM SINE™ compound and doxorubicin (dox; 0.1, 0.5, or 1 μM) for 20 hours and assayed for apoptosis by activated caspase 3. Apoptosis was induced in SINE™ compound /doxorubicin-treated cells in a dose-dependent manner ( $P < 0.021$ ).

**Figure 10. Stromal cell co-culture induced drug resistance.** H929 myeloma cells ( $5 \times 10^5$ ) co-cultured with HS-5 cells ( $5 \times 10^5$ ) are drug-resistant to CRM1 inhibitors ( $P=0.0001$ ) and doxorubicin ( $P=0.0002$ ) when used as a single agent compared with H929 cells grown in suspension. When compared to doxorubicin alone (columns 1 and 3 of the VC group (vehicle control)) ( $P<0.0001$ ) or the inactive trans-isomer KPT-185T ( $P<0.02$ ), both KPT-

185 and KPT-249 sensitized H929 cells when used in combination with doxorubicin. SINE™

compounds sensitized both suspension cells and co-cultured myeloma cells to doxorubicin.

**Figure 11: CRM1 inhibition sensitized MM cell lines and patient myeloma cells to doxorubicin but did not affect peripheral blood mononuclear or non-myeloma bone marrow mononuclear cells. A)** H929 myeloma cells were incubated concurrently with SINE™ compound (100 nM) and 1 μM doxorubicin over a time course of 4, 8, 16, 20, and 24 hours. MM cells demonstrated significant ( $P < 0.05$ ) apoptosis beginning at 8 hours with co-treatment of SINE™ compound and doxorubicin. **B)** Human peripheral blood mononuclear cells (PBMC) from normal donors ( $n=3$ ) were unaffected by treatment with SINE™ compound (300 nM) and were not sensitized to doxorubicin. **C and D)** CRM1 inhibitors sensitize patient myeloma cells ( $n=12$ ) to doxorubicin **(C)** but do not sensitize non-myeloma cells **(D)**. This indicates that SINE™ compound may specifically inhibit neoplastic cells in MM patients.

### Summary: Rationale

Drug resistance in multiple myeloma is correlated to the nuclear export of topo II $\alpha$  by the export receptor CRM1. Blocking nuclear export sensitizes drug-resistant human myeloma cells to chemotherapeutic agents. In a study published recently in our lab [46] we examined the cytotoxic effects of selinexor in MM cells. We showed by immunofluorescence microscopy and nuclear-cytoplasmic fractionation that these molecules were able to prevent nuclear export of the tumor suppressor protein p53 and the nuclear drug target topo II $\alpha$ . Cell viability data demonstrated that selinexor was effective as a single agent against human myeloma H929 and 8226 and HL-60 AML cells at nanomolar concentrations but was up to 239-fold less toxic to normal cells. Selinexor, when used in combination with the anti-MM agents doxorubicin, was found to sensitize drug-resistant MM cells in both the

high-density cell culture model and in co-culture with HS-5/GFP bone marrow stromal cells[46].

Combining selinexor with doxorubicin induced apoptosis and decreased cell viability of myeloma cells synergistically. The synergistic effects of selinexor with the myeloma drug doxorubicin was dose dependent, and time-course studies performed in high-density drug-resistant MM cultures showed that apoptosis was induced after a 8-hour co-treatment with doxorubicin/ selinexor. Normal human peripheral blood mononuclear cells were unaffected by selinexor treatment and were not sensitized to doxorubicin. In studies done on MM patient bone marrow mononuclear cells, selinexor-doxorubicin co-incubation synergistically induced activated caspase 3 in CD138/light-chain double-positive myeloma cell populations but not in CD138/light-chain double-negative non-myeloma cells, indicating that selinexor may specifically inhibit neoplastic cells in MM patients. We found that CRM1 protein levels are decreased by selinexor. Interestingly, CRM1 mRNA levels were increased by both selinexor and LMB even with the concurrent decrease of CRM1 protein found in selinexor -treated cells[46].

Recent publications on the effects of selinexor on AML have shown that selinexor has anti-proliferative effects on AML cell lines and primary AML samples. In addition, when used as a single agent, selinexor induced apoptosis and accumulation of p53 in the nucleus of AML cells. We found parallel results in human MM cell lines and in patient MM bone marrow mononuclear cells with selinexor as a single agent; in addition, selinexor sensitized MM cells both in vitro and ex vivo to doxorubicin[46].

High-density drug-resistant MM cell lines and cells made resistant by stromal cell co-culture were sensitive to selinexor treatment. Selinexor induced apoptosis both as a single agent and in combination with doxorubicin as compared to the inactive trans-isomer ( $P<0.02$ ) or DMSO vehicle control ( $P<0.0001$ ). Selinexor was found to sensitize both suspension cells and co-cultured myeloma cells to doxorubicin.

These data support the current clinical study investigating the combination of selinexor with doxorubicin in MM

### **1.5.2 Rationale for Starting Dose and Dosing Schedule**

In this trial, we propose weekly dosing of selinexor in combination with LD and dexamethasone. Dexamethasone will be given at a total of 40 mg weekly per myeloma therapy standard. The starting dose of LD will be 20 mg/m^2 IV on D1. Selinexor will be given orally on days 1, 8, and 15 of the cycle. The starting dose of selinexor will be 40 mg/m^2 (~68 mg) weekly, taking into account for the potential overlapping toxicities with LD (thrombocytopenia, nausea). In the ongoing Phase 1 study (KCP-330-001) in patients with hematological malignancies, a dose of 45 mg/m^2 twice weekly (90 mg/m^2 weekly) cleared DLT; currently dosing at 60 mg/m^2 (120 mg/m^2 weekly). Therefore, the starting dose in this study of 40 mg/m^2 selinexor twice weekly, based on prior regimens, would correspond to a weekly dose of 80 mg/m^2, which was found to be tolerable in prior studies. Of note, doses as low as 3 mg/m^2 have shown biological and clinical activity.

Importantly, our preclinical studies suggest synergism between doxorubicin and selinexor when selinexor is given prior to doxorubicin, and we have recommended a loading dose of selinexor for the first 2 weeks on the trial.

Of note, cohort 2m and 3m have used a one week (one dose of selinexor 80 mg) loading phase only.

The following dose levels will be evaluated in this trial:

Dose level	Number of selinexor doses during loading	LD IV on D1	Selinexor PO	Dexamethasone* PO D1, 8, 15
-1	4 (Days-14, -11,-7, -4)	20 mg/m 	40 mg D1, 8, 15	40 mg
1	4 (Days-14, -11,-7, -4)	20 mg/m 	40 mg/m  (~68 mg) D1, 8, 15	40 mg
2	4 (Days-14, -11,-7, -4)	20 mg/m 	80 mg D1, 8, 15	40 mg
1m	1 (day -7 only)	20 mg/m 	60 mg D1, 8, 15	40 mg
2m	1 (day -7 only)	20 mg/m 	80 mg D1, 8, 15	40 mg
3m	1 (day -7 only)	20 mg/m 	80 mg D1,3,8, 10	40 mg
4m	1 (day -7 only)	30 mg/m 	80 mg D1,3,8, 10	40 mg

[figure not shown]
\* For patients with intolerance to 40 mg of dexamethasone or who are older than 75 years, the starting dose of dexamethasone will be 20 mg on the same schedule

LD is administered at least 2 hours (but less than 4hours) after selinexor administration on day 1 of each induction cycle

[figure not shown]
Patients enrolled on cohort 2m will have a 1 week loading phase and selinexor will be administered on days 1,8,15 of the cycle (see below).

Dose level 2m was found to be the recommended phase II dose and will be the dose level used in the phase II / expansion cohort.

MCC 17814 Phase I/II of Selinexor in combination with LD and dexamethasone for Myeloma

Patients enrolled on cohort 3m and 4m will have a 1 week loading phase and receive Selinexor on days 1,3, 8, 10 of the cycle (see below)

After amendment 5, patients will start dosing on dose level 2m

### **1.5.3 Study Population and Sample Size**

Up to 47 patients with relapsed and refractory myeloma will be included in this trial: up to 24 patients on the phase I study and 23 on the phase II trial. Responses in 3 or more of the 13 patients treated at the RP2D will establish the rationale for enrollment of 16 additional patients.

### **1.5.4 Assessment for Response**

The uniform response criteria of the international myeloma working group (IMWG) will be used for response assessment (see Appendix A) [47].

## **2 OBJECTIVES**

### **2.1 Primary Objective**

For the phase I portion, the primary objective is to determine the safety and recommended phase II dose (RP2D) of selinexor in combination with LD and dexamethasone in patients with relapsed and refractory myeloma.

In the phase II portion, the primary objective is to evaluate the efficacy (overall response rate—partial response and better) of selinexor and LD and dexamethasone in patients with relapsed and refractory myeloma.

### **2.2 Secondary Objectives**

To estimate the progression-free (PFS), duration of response (DOR), and overall survival (OS) in patients with relapsed and refractory myeloma treated with this combination.

To estimate the clinical benefit rate (minimal response and better) of the combination in relapsed and refractory myeloma.

## **3 INVESTIGATIONAL PLAN**

### **3.1 Overview of Study Design and Dosing Regimen**

This is a investigator-sponsored phase I/II study to evaluate the effectiveness and tolerability of oral selinexor in combination with liposomal doxorubicin and dexamethasone in patients with relapsed and refractory multiple myeloma. This study will be conducted at H. Lee Moffitt Cancer Center and Research Institute, Wayne State University / Karmanos cancer center and Virginia Commonwealth University Massey Cancer Center.

After the initial screening visit and registration in the study, eligible patients will receive selinexor on day -7= at a dose of 80 mg in addition to dexamethasone 40 mg. After 1 week of dosing with selinexor and dexamethasone, patients will receive weekly selinexor at a starting dose of 80 mg (cohort 2m) in combination with liposomal doxorubicin at a starting dose of 20 mg/m^2, and dexamethasone at 40 mg orally weekly.

[figure not shown]
During the treatment period, patients will undergo physical examination and assessment of tumor response (paraprotein assessment) every 3 weeks per the IMWG uniform response criteria.

Patients will be treated until progression of disease or the development of unacceptable toxicities. All patients will then undergo a final visit (end of treatment visit).

### 3.1.1 Definition of Treatment Cycle and Duration

The study will consist of 4 phases. A screening phase, a loading phase, an induction phase (DLT evaluable period in the phase I), and maintenance phase.

#### Study Schema

Loading phase is 1 week with selinexor and dexamethasone. Induction cycles are repeated every 21 days. Patients will receive up to 8 cycles of selinexor in combination with liposomal doxorubicin and dexamethasone. After 8 cycles, patients experiencing a clinical benefit (stable disease or better) will continue on selinexor (administered at the tolerated dose orally once weekly) as a single agent until disease progression or unacceptable toxicity. Maintenance cycles are 28 days in duration.

Study drug administration may be delayed for toxicity according to protocol Section 8.

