	
treatment phase.
 
The dose escalation for the phase I will be as follow:
 
Dose level -1: 40mg on days 1,8, 15 in combination with 20 mg/m^2 LD
 
Dose level 1: 40 mg/m^2 (~68 mg) on days 1,8, 15 in combination with 20 mg/m^2 LD includes a 2 week loading phase (4 total doses in loading)
 
Dose level 2: 80 mg on days 1, 8, 15 in combination with 20 mg/m^2 LD (includes a 2 week loading phase (4 total doses in loading)
 
Dose level 1m: 60 mg on days 1, 8, 15 in combination with 20 mg/m^2 LD (Includes a single loading dose on day -7)
 
Dose level 2m: 80 mg on days 1, 8, 15 in combination with 20 mg/m^2 LD (Includes a single loading dose on day -7)
 
Dose level 3m: 80 mg on days 1,3,8, 10 in combination with 20 mg/m^2 LD (Includes a single loading dose on day -7)
 
Dose level 4m: 80 mg on days 1,3,8, 10 in combination with 30 mg/m^2 LD (Includes a single loading dose on day -7)
 
After amendment 5, patients will start dosing on dose level 2m
 
Intra-patient dose escalation
 
Intra-patient dose escalation of selinexor will be allowed at the discretion of the principal investigator and treating physician, provided that dose level has been found to be well tolerated(cleared DLT with 6 patients treated at that dose level). Inpatient dose escalation would only occur after patients have completed the first cycle and can also occur in the maintenance setting.
 
Maintenance phase:
 
After 8 cycles of therapy with selinexor, LD, and dexamethasone, patients will be eligible to proceed on maintenance with the tolerated dose of weekly selinexor and dexamethasone until disease progression. In maintenance, cycles are 28 days.
 
Definition of dose limiting toxicity (DLT)
 
DLT is defined as any of the following occurring in the first cycle (excluding the selinexor loading period from D-14 to D-

--	--

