	
optimum design, there would be a 90.7% chance of detecting a tumor response rate of at least 40% and a response rate of 15% or less would lead to the conclusion that the regimen lacks antitumor activity at a 0.05 significance level. The probability of early stopping (in stage I) is 0.058 if the true response rate of the combination is 40%.
 
Dose Schedule
 
Loading phase: Patients will receive selinexor at 80 mg on D-7 orally. This dose was shown to be tolerable in a study of patients with chronic hematologic malignancies including myeloma (NCT01607892). In addition, patients will receive dexamethasone 40 mg on day -7. The loading phase lasts 1 week.
 
Induction phase: Patients will be treated initially with selinexor at the RP2D PO weekly dose (on days 1, 8, 15) (or twice weekly dosing on cohort 3m and 4m), liposomal doxorubicin at the RP2D IVPB on D1 (at least 2 hours (and no longer than 4 hours) after the selinexor dose), and dexamethasone 40 mg PO weekly (on days 1, 8, 15). Cycles are repeated every 3 weeks (21 days) and patients will receive a maximum of 8 cycles of therapy with this combination. For patients with prior doxorubicin exposure, after a total dose of 450 mg/m^2, patients will be required to have cardiac assessments (echocardiograms or MUGA) every 2 cycles. Any patient with a decrease in ejection fraction of <math>\geq</math> 20% from baseline will have LD discontinued.
 
Maintenance phase: After 8 cycles of therapy with selinexor, LD and dexamethasone, patients will be eligible to proceed on maintenance with the tolerated dose of selinexor and dexamethasone until disease progression. Cycles are repeated every 28 days
 
Discontinuation Criteria:
 
At the discretion of the Investigator, the investigator may remove a patient from the study for the following reasons:
 

• Due to disease progression

• Noncompliance with study procedures

• Patient no longer consents to participate in the study

• Intercurrent illness that interferes with study assessments

• Investigator discretion

• Incidence or severity of AEs in this study indicates a potential health hazard to the patient

• Termination of the study by the sponsor

--	---

	
 
• Pregnancy
 

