
Duration of Treatment
	
After 8 cycles of the combination of LD, dexamethasone, and selinexor, patients may continue to receive selinexor and dexamethasone until disease progression or occurrence of an unacceptable toxicity in the phase I and II.

Inclusion /Exclusion Criteria
	
Inclusions:
 
 
1. Written informed consent in accordance with federal, local, and institutional guidelines
 
2. Age <math>\geq</math> 18 years
 
3. Patients with relapsed and refractory multiple myeloma who have received at least 2 prior therapies which must include lenalidomide and a proteasome inhibitor. Patients must have disease refractory to the most recent therapy. Refractory myeloma is defined as progressive disease during or within 60 days of last therapy. Patients must have previously received or be ineligible for (or refused) autologous stem cell transplant.
 
4. Patients must have measurable myeloma paraprotein levels in serum (<math>\geq</math> 0.5 g/dL) or urine (<math>\geq</math> 0.2 g excreted in a 24-hour urine collection sample) or by free light chain (involved free light chain greater than 100 mg/L).
 
5. ECOG performance status of 0-1. ECOG 2 allowed if due to bone disease.
 
6. Must have an echocardiogram or MUGA indicating LVEF <math>\geq</math> 50% within 42 days prior to first dose of study drug.
 
7. Adequate hematological function:             
 
a. In the phase I portion: absolute neutrophil count (ANC) <math>\geq</math>1000/mm^3, platelet count <math>\geq</math>50,000mm^3. GCSF is not allowed during screening or during the first cycle for phase I patients.
 
b. In the phase II portion, if the patient has significant bone marrow involvement (BM plasma cells <math>\geq</math> 50%), platelet count <math>\geq</math>30,000mm^3 and (ANC) <math>\geq</math> 1000/mm^3 are required. GCSF is allowed during screening and therapy for all phase II patients. Alternatively, with less BM involvement, an absolute neutrophil count (ANC) <math>\geq</math> 1000/mm^3, and platelet count <math>\geq</math>50,000mm^3 are required.
 
 
 
8. Adequate hepatic function within 14 days prior to loading phase (day -14): total bilirubin <2 times the upper limit of normal (ULN) (except patients with Gilbert's syndrome who must have a total bilirubin of
 

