### 3.1.3 Criteria to Proceed with a New Cycle of Therapy During Maintenance

It is expected that responding patients (stable disease or better) will proceed to maintenance therapy with selinexor and dexamethasone, and typically this would be associated with an improvement of disease-related parameters. In addition, long-term maintenance therapy needs to be associated with less long-term toxicities. To start a new cycle of maintenance, the following criteria must be met:

ANC is greater or equal to  $1,000/\text{mm}^3$

Platelet count is greater or equal to  $30,000/\text{mm}^3$

In addition, non-hematologic toxicities must have recovered as described in Section 6.1

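### Maintenance is selinexor alone in Section 3.1.1 but selinexor with dexamethasone in the synopsis and Section 3.1.3, and nothing says which text governs

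*Combined protocol and SAP*

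**What the plan says.** Section 3.1.1 (Study Schema) keeps patients whose disease is at least stable after eight cycles on once-weekly selinexor "as a single agent until disease progression or unacceptable toxicity".

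Four other statements name two drugs:

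- Synopsis, Study Design, maintenance paragraph: "patients will be eligible to proceed on maintenance with the tolerated dose of weekly selinexor and dexamethasone until disease progression".
- Synopsis, Dose Schedule: "patients will be eligible to proceed on maintenance with the tolerated dose of selinexor and dexamethasone until disease progression".
- Synopsis, Duration of Treatment: "patients may continue to receive selinexor and dexamethasone until disease progression or occurrence of an unacceptable toxicity in the phase I and II".
- Section 3.1.3: responding patients, which there includes stable disease, are expected to "proceed to maintenance therapy with selinexor and dexamethasone".

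Section 9.1.1.3 makes a corticosteroid a required part of the regimen and does not exempt maintenance.

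On the analysis side, Section 11.6 counts PFS from the start of treatment and follows patients for progression and survival until the study ends. Section 11.1.2 lists duration of response and safety as secondary endpoints. Section 11.3 defines a per-protocol population that leaves out patients with major protocol violations.

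**The concern.** Dexamethasone is one of the three study drugs. The protocol therefore gives two different answers to what a patient takes from the ninth cycle onward. A site that follows the Study Schema gives one drug, and a site that follows Section 3.1.3 gives two.

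Three things are at stake. First, PFS and duration of response continue into maintenance, so the part of each that accrues there may describe a mixture. Second, the same holds for maintenance safety. The protocol's own supportive-care text (Sections 9.2.1, 9.2.2 and 9.2.3.1) credits glucocorticoids with helping appetite, fatigue and control of emesis, so their presence or absence could plausibly change tolerability. Third, each maintenance regimen complies with one section and departs from another, so the per-protocol rule in Section 11.3 cannot be applied to maintenance patients.

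**Working it through.** **Step 1: the statements side by side.**

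| Place | Selinexor | Dexamethasone |
|---|---|---|
| Section 3.1.1, Study Schema | yes, weekly | no |
| Synopsis, Study Design (maintenance) | yes, weekly | yes |
| Synopsis, Dose Schedule | yes | yes |
| Synopsis, Duration of Treatment | yes | yes |
| Section 3.1.3 | yes | yes |
| Section 9.1.1.3 | not addressed | corticosteroid required, no phase excepted |

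The count is one statement for selinexor alone against four for the pair, with Section 9.1.1.3 leaning toward the four. A count does not establish which text governs.

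**Step 2: is the odd statement visibly obsolete?** No. The same Study Schema paragraph gives a one-week loading phase. That is the current schedule; dose levels 1 and 2 in Section 1.5.2 had four loading doses from day -14. A site has no reason to read the paragraph's maintenance clause as superseded.

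**Step 3: does other text settle it?** No.

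- The study calendar (Section 5) has no dexamethasone row. Footnote 16 says only that dexamethasone is taken at home.
- Section 8.3.3 lists dexamethasone on days 1, 8 and 15, which fits the 21-day induction cycle. No schedule is given for the 28-day maintenance cycle.
- Section 11.6 neither defines duration of response nor mentions dexamethasone in maintenance.

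**Step 4: when maintenance starts.** The inputs are eight induction cycles of 21 days and a one-week loading phase (Section 3.1.1).

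- Induction: 8 x 21 = 168 days.
- With loading: 168 + 7 = 175 days = 25 weeks, or 175 / 30.4375 = 5.7 months, if there are no delays.

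Duration of response has a different clock. Taking it from first response (an assumption, since it is undefined), a response at the end of cycle 2 occurs at 7 + 2 x 21 = day 49, so it has run 175 - 49 = 126 days when maintenance begins.

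**Step 5: how many patients.** The documents do not give the proportion reaching maintenance. The only related figure is the treatment period of about 3 months in Section 3.2, which is itself shorter than the 168 days of planned induction. As an illustration only, with exponential time on treatment and the 29 phase II patients:

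- 3 months as the mean: exp(-5.75 / 3) = 0.147, and 29 x 0.147 = about 4 patients.
- 3 months as the median: 0.5^(5.75 / 3) = 0.265, and 29 x 0.265 = about 8 patients.
- An assumed 30% to 60% instead: 29 x 0.30 = about 9, and 29 x 0.60 = about 17 patients.

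The spread from 4 to 17 shows that the number is not determined.

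**Step 6: the primary design.** The rule is to continue with at least 3 responses in 13 and declare activity with at least 8 in 29. With X1 ~ Bin(13, p) and X2 ~ Bin(16, p):

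- P(stop early) = P(X1 <= 2).
- P(declare active) = sum over x = 3 to 13 of P(X1 = x) P(X2 >= 8 - x).

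At p = 0.40 these give 0.0579 (plan: 0.058) and 0.9069 (plan: 90.7%). At p = 0.15 the second gives 0.0500 (plan: 0.05). No input depends on the maintenance regimen.

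**The case against.** The strongest reply is that this is a wording slip with little effect on inference. Four statements agree, so most sites would probably read it the same way. PFS and OS are single-arm Kaplan-Meier estimates with no control. Dexamethasone exposure already varies by design, through the 20 mg start for some patients, dose reductions and discontinuation for toxicity. Section 14.3.2 requires procedures to be agreed at start-up and treatment to be reviewed on regular calls, Section 14.3.3 requires monitoring for compliance, and Section 8.1.3 has dose modifications entered in the CRF.

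Much of this stands as a limit on size. These controls lower the risk that sites diverge, but they cannot say which section a compliant site should follow. Variation through toxicity-driven reductions is also different from variation because the protocol names two regimens.

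Stronger readings that a reader might infer are not supported:

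- **That the sites did give different regimens.** Three sites make this possible; nothing in the documents shows it.
- **That a third to a half or more of the phase II patients are affected.** No such proportion is given, and it sits badly with the 3-month treatment period in Section 3.2. Nor does everyone who finishes eight cycles go on: Section 3.1.1 requires stable disease or better, and the synopsis wording is permissive.
- **That all PFS and response-duration time beyond about six months is affected.** Some of that time belongs to patients off treatment without progression or still in delayed induction, and duration of response need not share the PFS clock.

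**Conclusion.** The contradiction is certain and sits in operative text, so the plan is wrong as written. It is more than clerical, because it decides what patients receive during time that counts toward three secondary endpoints and leaves protocol compliance in maintenance undefined.

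Its reach is limited. It touches only time accrued on maintenance, which begins at the earliest about 175 days after the first loading dose, assuming the one-week loading phase and no delays. The number of patients cannot be computed from the documents. A mixture of regimens is possible rather than shown. A reader might infer that the sample size or error rates of the primary endpoint are in doubt; they are not, since the stated figures reproduce without any maintenance input. The documents give no basis here for saying which maintenance regimen is the intended one.

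**What to change.** Reconcile Section 3.1.1, Section 3.1.3, the three synopsis entries and Section 9.1.1.3 so that one maintenance regimen is stated throughout. The sponsor decides which.

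Make sure the CRF records which study drugs each patient received in maintenance. This is worth checking because concomitant medication is not collected in the eCRF (Section 5, footnote 19), so a steroid regarded as outside protocol maintenance might go unrecorded.

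If both regimens turn out to have been used, report how many patients received each. Any description of outcomes by regimen should start from a landmark at the beginning of maintenance. Splitting PFS from the start of treatment by maintenance regimen would give both groups guaranteed event-free time, because a patient must complete induction without progression to be classified. Even the landmark description would rest on few patients and could be confounded with site, so it should stay descriptive.

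The cost is about one sentence in the next amendment, conforming edits where needed, and at most one CRF field. Sample size and the primary analysis do not change.
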